9.5.2 Visits at months 1 (+/- 7 days) and 6 (+/- 7 days)

Visits at months 1 and 6 are safety visits after study drug initiation. Only liver function tests (LFTS), complete blood count (CBC) and pregnancy test (in women of child-bearing potential) will be obtained. Adverse events will be assessed/reviewed. Abbreviated medical history and a physical exam will be performed to assess any changes in medical conditions or medications. If feasible, blood may be obtained at a local lab and results faxed to NIH and a phone call from the research coordinator or investigators will assess adverse events.

9.5.3 Visits at 3 (+/- 7 days) and 8 months (+/- 7 days)

Subjects will undergo a physical exam and blood will be drawn for biomarkers and safety labs. SF-36, PGA, disease activity and vascular measurements will be obtained. Abbreviated medical history will be performed to assess any changes in medical conditions or medications. Any leftover study drug will be collected and drug accountability performed. No additional study drug will be dispensed at these visits. PET exams will be performed in 15 patients initially randomized to placebo and 15 patients initially randomized to pioglitazone and the investigators will be blinded to this. PET studies will only be performed at baseline and month 3. A urine analysis will be obtained at the end of the study to assess for hematuria.

The minimum time between baseline and visit 3-month and between visit 5 month and visit 8 month will be 75 days and the maximum 105 days. Overall, total study duration will not exceed 9 months (+/- 1 month).

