8 STUDY DESIGN AND METHODS

This will be a single-center, randomized, double-blind, placebo-controlled, crossover, proof-of-concept treatment trial enrolling 100 SLE patients including replacements due to screen failures and withdrawals. If a patient drops out of the study before completion both arms, another patient may be enrolled so that up to 75 patients complete the study. They will be treated for 3 months with 45 mg daily pioglitazone or placebo, undergo an 8 week washout period, then undergo crossover to the other arm for 3 additional months. Throughout the study, functional, anatomical and blood biomarkers of vascular damage, atherosclerosis risk and SLE activity will be collected. Pioglitazone has been chosen over rosiglitazone because it appears to have a significantly better safety profile regarding CV effects and lipid profile alterations⁹³, based on our experience in the rheumatoid arthritis (RA) trial⁵ and the small pilot study published by

another group that showed improvement in some metabolic parameters in SLE⁹², as well as our preliminary data which indicate improvement of vasculogenesis by pioglitazone but not rosiglitazone⁹⁴ in human SLE. We also have significant experience using this drug due to the recently completed clinical trial in RA³. The dose and study time period have been selected based on pioglitazone's macrovascular protective effects⁷⁴ and to allow detection of meaningful changes in endothelial function and disease activity, respectively. This is also based on the dose and study time period used in the RA trial, which showed significant effects on arterial stiffness, metabolic parameters, inflammatory markers and RA disease activity⁵.

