TZD studies indicate improvements on endothelial function from within a few weeks to a couple of months. Previous crossover studies assessing pioglitazone's role in endothelial function, insulin resistance and inflammation have used treatments from 6-12 weeks with washout periods of 4-6 weeks^{68, 72, 95}. In our studies in RA, 3 months was sufficient to observe significant improvements in arterial compliance and disease activity⁵. These washout periods appeared sufficient to avoid carryover effects and, indeed, in the RA trial we found no evidence of carryover effect after the same washout period⁵. Carryover issues will also be addressed by randomizing the sequence of placebo and pioglitazone treatment. Previous studies did not reveal that the sequence (i.e. placebo followed by pioglitazone vs. pioglitazone followed by placebo) had any effect on the observations⁶⁸. The study will take approximately 5 years to complete. Figure 2 represents the study sequence.

[figure not shown]

Figure 2: Overall Study Schematic

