9.5 Study Visits

9.5.1 *Baseline visit and 5-month +/- 7 days (post-washout) visit*

- a. Baseline visit will include medical history. The baseline and 5-month (post-washout) visits will consist of a physical exam, and blood draw for biomarkers (Table 3). SF-36, PGA, disease activity (BILAG 2004, SLEDAI-2K) and vascular measurements will be determined and subjects will be issued a 3-month supply of blinded study drug or placebo with instructions. The first week of each treatment arm, patients will take two 15 mg capsules of pioglitazone daily (30 mg total daily dose) and, if no significant side effects develop (primarily fluid retention), will increase to three 15 mg capsules (45 mg total daily dose). Subjects will be instructed to follow the same titration for the placebo arm. Patients will be called prior to increasing the dose to 45 mg to question patients about rapid weight gain (>5 pounds in a week), significant edema or other side effects. Patients will be called 1-2 weeks after increasing dose to 45 mg daily to assess tolerability. If 45 mg dose is not well tolerated but the 30 mg dose is well tolerated, dose will be decreased back to 30 mg daily for duration of trial. PET/CT exams will be performed in 15 patients initially randomized to placebo and 15 patients initially randomized to pioglitazone and the investigators will be blinded to this. PET/CT studies will only be performed at baseline and month 3. Subjects can opt out of the PET/CT scan and still participate in the study. Patients will be asked to participate at baseline until we reach 15 patients/group. If a patient is found to have an acute infection at the baseline visit, they will be given antibiotics and their next visit will be scheduled for no more than 4 weeks later, at which time they will start the study medication. We will repeat only baseline clinical labs at this extra visit; we will not repeat PET/CT, vascular function studies or research sample collection. If a patient has an abnormal lab result at the baseline visit that requires a repeat, the patients next visit will be scheduled no more than 4 weeks later, at which time if the abnormal lab has improved or normalized they will

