10.4 Blinding, Packaging, Labeling and Storage

Study agent (15 mg pioglitazone or placebo) will be packaged in identical vials each containing 300 capsules. Both study agents will be blinded using identical-looking capsules prepared by a vetted vendor selected by the NIH Pharmaceutical Development Service (PDS). Each vial will be labeled with a treatment number specific to the subject. A 300 capsule (one vial) supply of study agent will be given to each subject at enrollment at the baseline visit and at month 5. The amount of study agent dispensed will be sufficient to last from baseline to month 3, and from month 5 to month 8. The randomization code will be provided by the Clinical Center Research Pharmacy, as mentioned above. Emergency unblinding will occur in the case of a serious adverse event (SAE) that is considered potentially secondary to the drug. Unblinding will be performed by PDS. Only the pharmacists will be unblinded throughout the trial. The subjects, the investigators, and the study site staff will remain blinded to study medication assignment during the entire study period. Compliance with study treatment and pill counts will be performed by the research nurse/study coordinator and this information will be provided to PDS as well.

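### The baseline-to-month-3 interval has two visit windows with no rule on which governs; at its 105-day maximum one 300-capsule vial falls short, and the windows do not secure the stated 8-week washout.

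*Combined protocol and SAP*

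**What the plan says.** The protocol makes five statements that bear on timing.

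- **Months 3 and 8, section 9.5.3.** The heading reads "Visits at 3 (+/- 7 days) and 8 months (+/- 7 days". The closing paragraph of the section says that the minimum time from baseline to month 3, and from month 5 to month 8, "will be 75 days and the maximum 105 days". It also caps total study duration at 9 months, give or take one month.
- **Month 5, section 9.5.1.** The heading reads "Baseline visit and 5-month +/- 7 days (post-washout) visit".
- **Washout, section 8.** After the first 3-month period, patients "undergo an 8 week washout period, then undergo crossover to the other arm for 3 additional months". No minimum or tolerance is given.
- **Carryover, section 8.** The section cites earlier pioglitazone crossover studies with washouts of 4 to 6 weeks as adequate, and adds that "in the RA trial we found no evidence of carryover effect after the same washout period".
- **Supply, section 10.4.** Each patient receives one 300-capsule vial at baseline and one at month 5. "The amount of study agent dispensed will be sufficient to last from baseline to month 3", and likewise from month 5 to month 8. Table 3 shows dispensing only at those two visits, and section 9.5.3 rules out dispensing at months 3 and 8.

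Under section 9.5.1, patients take two capsules daily in the first week of each arm and then three daily if tolerated.

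**The concern.** A month-3 visit on day 75 or day 105 is allowed by one sentence of section 9.5.3 and out of window by its heading, so whether it is a protocol deviation depends on which line is read.

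Two other stated properties rest on the same windows. One is that the vial lasts the whole treatment period, so that patients are on drug when vascular function is measured. The other is that 8 weeks separate the periods. The month-5 visit is described as post-washout, but its window is given in calendar months and is not tied to the end of period-1 dosing.

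The washout matters because the month-5 measurement enters the section 11 analysis as the second baseline. In patients who take pioglitazone first, residual drug effect would affect that baseline and possibly the placebo period. Section 11 assesses carryover overall but does not use the length of each patient's washout.

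**Working it through.** **Inputs.** Windows from sections 9.5.1 and 9.5.3; an 8-week washout = 56 days (section 8); two capsules daily for 7 days, then three daily (section 9.5.1); 300 capsules per period (section 10.4). Two assumptions are needed because the documents are silent: a month is 30 to 30.44 days, and month 5 is counted from baseline, as the visit names in Table 3 suggest.

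**1. Do the windows agree?**
- Baseline to month 3: 90 - 7 = 83 to 90 + 7 = 97 days (30-day months), or about 84 to 98 (30.44-day months). Against 75 to 105, these differ by about a week at each end.
- Month 5 to month 8, with +/-7 at both visits: 90 - 14 = 76 to 90 + 14 = 104 days, or about 77 to 105. This nearly coincides with 75 to 105.

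The conflict is therefore in period 1.

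**2. Does the vial last?** Capsules needed over D days = 2 x 7 + 3 x (D - 7) = 14 + 3(D - 7).

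| D (days) | Needed | Left from 300 |
|---|---|---|
| 90 | 263 | 37 |
| 98 | 287 | 13 |
| 102 | 299 | 1 |
| 103 | 302 | -2 |
| 105 | 308 | -8 |

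The sufficiency statement is reproduced at the nominal 90 days and throughout the +/-7 window for month 3. It fails on days 103 to 105, where a fully adherent patient on three capsules has up to 105 - 102 = 3 days without drug. A patient kept on two capsules throughout needs 2 x 105 = 210 and has 90 to spare. In period 2 the +/-7 windows by themselves already allow 104 to 105 days, which needs 305 to 308 capsules.

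**3. Is the washout 8 weeks?** Visit-to-visit washout = month-5 day minus month-3 day. The month-5 window is day 143 to 157 (30-day months) or about day 145 to 159 (30.44-day months).
- Nominal: 150 - 90 = 60, or about 61 days. The stated 8 weeks is reproduced.
- Both visits within +/-7, month 3 late and month 5 early: 143 - 97 = 46, or about 47 days.
- Month 3 on day 105, month 5 earliest: 143 - 105 = 38, or about 40 days.
- Month 3 on day 105, month 5 latest: 157 - 105 = 52, or about 54 days.
- Last month-3 day that still leaves 56 days: 157 - 56 = 101, or about day 103.

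Time off drug differs from visit-to-visit time if the vial ran out after day 102. It is then 143 - 102 = 41 (about 43) days at the earliest month-5 date and 157 - 102 = 55 (about 57) at the latest.

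**4. The other anchor.** If month 5 is set 8 weeks after the actual month-3 visit, a day-105 visit puts month 5 on day 105 + 56 = 161. The washout holds, and 105 + 56 + 105 = 266 days (8.7 months) respects the duration cap. But day 161 is later than day 157 to 159, so month 5 misses its own window.

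**Sensitivity.** With 28-day months the nominal washout is exactly 56 days. The +/-7 minimum becomes 42 days, and the range after a day-105 visit becomes 28 to 42 days.

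**The case against.** The strongest reply has four parts.

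- **The wide rule may not be meant to override the narrow one.** If both apply together, +/-7 binds for month 3. The period-1 supply then suffices, and 56 days can always be scheduled, because the latest month-3 visit leaves 60 to 61 days before the month-5 window closes. This stands as a possible reading, but the text does not state it. Even so, 46 to 47 days remains permitted.
- **A short washout is not evidence of carryover.** Section 8 treats 4 to 6 weeks (28 to 42 days) as sufficient in earlier studies. The 38-day extreme is 5.4 weeks, inside that range, and 46 to 47 days exceeds it. Section 11 also plans a carryover assessment and uses both baselines. This stands. A reader might infer that the crossover contrast is compromised; the documents do not support that.
- **The supply gap and the washout gap partly offset each other.** A reader might infer that nobody seen on day 105 can have 8 weeks off drug. That is true only visit to visit. A full-dose patient who ran out after day 102 can reach 55 to 57 days. Patients with capsules left on day 105 have no supply problem but at most 52 to 54 days of washout.
- **The effect is small.** The shortfall is at most 8 capsules, on days 103 to 105, at full adherence on three capsules. This also stands. The documents give no basis for estimating how often such late visits would occur.

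**Conclusion.** The point holds as a minor inconsistency with a cheap remedy. Section 9.5.3 gives baseline to month 3 two windows and does not say which governs; a reader who extends this to all visits goes too far, because for months 5 to 8 the rules nearly coincide. At the permitted 105 days the supply statement in section 10.4 fails by 8 capsules for a fully adherent patient on the two-then-three schedule.

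The 8-week washout holds nominally but is not secured. With month 5 counted from baseline and months of 30 to 30.44 days, it can be 46 to 47 days within the +/-7 windows and 38 to 54 days after a day-105 visit. Counted instead from the actual month-3 visit, the washout is kept and the month-5 window is broken, so one stated rule gives way under either anchor.

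What is weakened is the appeal to the same washout as the rheumatoid arthritis trial, which the windows do not guarantee for every patient. Carryover is not shown, and no sample-size, alpha or power figure is affected.

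**What to change.** 1. Reconcile sections 8, 9.5.1, 9.5.3 and 10.4 so that one window governs each visit and agrees with the stated washout and supply. State the day from which month 5 is counted and how many days a month has. Which schedule is right is for the investigators to decide.
2. In section 10.4, either state that 300 capsules cover at most 102 days on the full two-then-three schedule, or bring the maximum interval and the supply into agreement.
3. Record the actual time from the last period-1 dose to the month-5 visit as a derived variable.
4. Prespecify in section 11 a sensitivity analysis of the primary treatment contrast by actual washout, below versus at least the stated 8 weeks. Report it as supportive, since washout length is not randomised, and show it by sequence, because residual drug can arise only in patients who took pioglitazone first.

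The cost is wording, one derived variable and one sensitivity analysis.

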9.5.4 Unscheduled Visits

Subjects will undergo a physical exam and abbreviated medical history will be performed to assess any changes in medical conditions or medications. Reason for the visit will be assessed related to AE, flare or study unrelated procedure/visit. Blood may be drawn for clinical and safety labs when deemed appropriate by the study investigator. We may also perform a urine test called urine analysis. Research blood may also be drawn for biomarkers as needed.

10 MONITORING SUBJECTS AND CRITERIA FOR WITHDRAWAL

10.1 Patient Withdrawal and Termination Criteria.

Subjects will be informed that they may withdraw or be excluded from the study at any time. Our intention is to maintain stable doses of immunosuppression and antimalarials for the

duration of the trial. On occasion, doses are adjusted to treat SLE activity. While not ideal, we anticipate that over the duration of 8 months, outside providers may want to adjust or add new immunosuppressive therapy. In the event of these changes, each of these instances will be reviewed by the Principal Investigator to determine continuation or withdrawal from the trial to maintain scientific integrity.

The following conditions will require the discontinuation of study agent:

1. Subjects may voluntarily withdraw at any point
2. Flares not responding to the treatment above or if, in the opinion of the responsible investigator, the subject needs immediate immunosuppressive therapy that is not allowed in the protocol
3. Any Grade 4 adverse event that is unexpected and at least possibly, probably or definitely related to study drug
4. More than 1 “no-show” for a visit
5. Becoming pregnant after baseline visit. The subject will be followed for the outcome of the pregnancy.
6. Any other reason that, in the opinion of the responsible investigator, poses unacceptable risk to the subject.
7. Nevertheless, LFTs will be monitored on all patients at each study visit and those patients with LFTs >2x upper limit at Screening visit will be excluded. If during the trial, LFTs increase to > than 3x fold the upper limit of normal (ULN), levels will be rechecked within 36 hours and if elevation >3 ULN persists and there are not alternative etiologies, therapy will be discontinued. If LFTs are elevated >2 but < 3x ULN (after confirming within 48 hours), we will investigate etiology of liver enzyme elevation and cautiously reinstate therapy if alternative etiology is found. For patients with NAFLD that are enrolled, based on recent clinical trials that have been published (Cusi K et al. Annals of Internal Medicine 2016) assessing the role of long-term pioglitazone treatment for nonalcoholic steatohepatitis, we will include only patients that have LFTs < 3 times ULN. If there is an increase to >3 times ULN once study drug starts during monitoring (confirmed within 24 hours), drug will be stopped.

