Unlikely (must have at least 2)	
 1) does not have temporal relationship to intervention 2) could readily have been produced by the subject's clinical state 3) could have been due to environmental or other interventions 4) does not follow a known pattern of response to intervention 5) does not reappear or worsen with reintroduction of intervention
Possible (must have at least 2)	
 1) has a reasonable temporal relationship to intervention 2) could not readily have been produced by the subject's clinical state 3) could not readily have been due to environmental or other interventions 4) follows a known pattern of response to intervention
Probable (must have at least 3)	
 1) has a reasonable temporal relationship to intervention 2) could not readily have been produced by the subject's clinical state or have been due to environmental or other interventions 3) follows a known pattern of response to intervention 4) disappears or decreases with reduction in dose or cessation of intervention
Definite (must have all 4)	
 1) has a reasonable temporal relationship to intervention 2) could not readily have been produced by the subject's clinical state or have been due to environmental or other interventions 3) follows a known pattern of response to intervention 4) disappears or decreases with cessation of intervention and recurs with re-exposure

12.3.8.3 Expectedness of Adverse Events:

For purposes of regulatory reporting, the medically responsible investigator will determine whether an AE or SAE is expected or unexpected. Expected adverse events are those adverse events that are listed or characterized in the Package Insert or in the Physicians' Desk Reference.

Unexpected adverse events are those not listed in the Package Insert (P.I.) or Physicians' Desk Reference (PDR), published medical literature, protocol, and informed consent document or not identified. This includes adverse events for which the specificity or severity is not consistent with the description in the P.I., PDR, published medical literature, protocol and informed consent. For example, under this definition, hepatic necrosis would be unexpected if the P.I. only referred to elevated hepatic enzymes or hepatitis.

For consistency of labeling and categorizing adverse events, the NCI CTCAE, Version 4.0 will be used in this study.

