The PI is responsible for summarizing all serious adverse events and adverse events at least possibly related to the research procedure and interventions at the time of Continuing Review.

12.3.13 Reporting of Deaths:

All deaths that have occurred among study participants since the previous review will be summarized at the time of continuing review.

12.3.14 Reporting Waivers:

Waiver of Reporting to the IRB of anticipated minor protocol deviations, adverse events and deaths due to underlying disease or population under study unless determined to be an Unanticipated Problem.

- Non-unanticipated problems (UP)/ adverse events will not be reported to the IRB unless they occur at a rate greater than that known to occur in patients with SLE. If events are occurring substantially more frequent than would be anticipated in typically treated patients with SLE, they will also be reported to IRB. The following anticipated adverse events will not be reported to the IRB unless they occur at a severity greater than that known to occur in patients taking pioglitazone: lower extremity edema, decrease in Hb which is less than 1.5 g/dl, weight gain <5 pounds/week. Examples of expected adverse events include those events detailed in the Investigator's protocol for pioglitazone and

in the pioglitazone drug insert. No more than a total gain of 15% weight gain if associated with signs and symptoms of volume overload such as shortness of breath on exertion, paroxysmal nocturnal dyspnea or elevated jugular venous pressure will be allowed for the total duration of the study. If patient gained weight during study due to other reasons such as lifestyle changes or increase in Prednisone dose or other specific reasons and the patient is not at risk of health compromising condition, these reasons will be documented in CRIS and will not be reported as Unanticipated Problems. Patient will be advised to lose weight through NIH nutrition consults or exercising. If the rate of these events exceeds the rate specified in the protocol or investigator's brochure the events will be classified and reported as though they are Unanticipated Problems.

12.3.15 Adverse Event, Protocol deviation and Unanticipated Problem Assessment and Follow-up:

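### Outside the liver-test rule, Section 10.1 item 3 makes stopping mandatory for a related Grade 4 event only if the event is also 'unexpected', a term defined only for regulatory reporting

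*Combined protocol and SAP*

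**What the plan says.** Section 10.1 of the combined protocol and SAP gives seven conditions under which study agent must be discontinued. Three matter here.

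- **Item 3**, the rule tied to event grade: "Any Grade 4 adverse event that is unexpected and at least possibly, probably or definitely related to study drug".
- **Item 6**, the residual rule: "Any other reason that, in the opinion of the responsible investigator, poses unacceptable risk to the subject".
- **Item 7**, the liver rule: on a repeat test, "if elevation >3 ULN persists and there are not alternative etiologies, therapy will be discontinued".

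Section 10.1 does not define 'unexpected'. The definition is in 12.3.8.3, which opens: "For purposes of regulatory reporting, the medically responsible investigator will determine whether an AE or SAE is expected or unexpected". It continues: "Expected adverse events are those adverse events that are listed or characterized in the Package Insert", with the Physicians' Desk Reference as an alternative source. Unexpected events are those absent from the insert, that reference, the literature, the protocol and the consent form. A further clause widens the unexpected class: "This includes adverse events for which the specificity or severity is not consistent with the description" in those sources.

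Section 12.3.14, on reporting waivers, adds: "Examples of expected adverse events include those events detailed in the" protocol and the drug insert.

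**The concern.** Expectedness separates known reactions from new ones, which is what a reporting rule needs. It does not measure danger to the subject. On the fallback severity chart in 12.3.8.1, Grade 4 means that the patient was at immediate risk of death. A related event at that level is no safer because the label already mentions it. When a reporting term is used as a condition for stopping drug, a known and life-threatening drug effect may escape the mandatory stop that a new one would trigger.

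The condition bears mainly on fluid and cardiac events, which the protocol describes as risks of this drug class. Section 6.6 calls weight gain, leg edema and dyspnea expected effects of the class. Table 2 shows edema in 6 subjects on pioglitazone and 0 on placebo in the earlier rheumatoid arthritis trial.

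**Working it through.** The plan has no figure to reproduce. The check sets the rules side by side.

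**Step 1: the logic of item 3.** The stop needs three things together: Grade 4, unexpected, and at least possibly related. An event that is Grade 4, related and expected does not meet it.

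**Step 2: what else in 10.1 could force a stop.** Items 1 and 4 concern voluntary withdrawal and missed visits. Item 2 concerns flares, item 5 pregnancy and item 7 liver tests. None names a cardiac or fluid event. For a non-hepatic event classed as expected, only item 6 remains. Item 6 is also a required stop, but only once the investigator judges the risk unacceptable.

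**Step 3: could such an event be classed as expected?** Two lines of text pull in opposite directions.

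| Text that points to expected | Text that points to unexpected |
|---|---|
| 12.2.2.6 cites a boxed warning on worsening of congestive heart failure with this drug class | 12.2.2.6 describes edema only as mild to moderate |
| 12.3.8.3 counts any event listed or characterized in the insert as expected | 12.3.8.3 makes an event unexpected if it is more severe or more specific than described |
| 12.3.14 counts events detailed in the protocol as examples of expected events | 12.2.2.6 closes by expecting no adverse cardiovascular outcomes; 9.3 excludes current NYHA class II to IV heart failure and ejection fraction below 45% |

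The right-hand column is the stronger for new, life-threatening heart failure in this population. The classification still belongs to the investigator, and the left-hand reading is open.

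**Step 4: do other controls close the gap?** Section 9.5.1 has calls around the dose increase and a reduction to 30 mg if 45 mg is not tolerated. Section 12.2.2.6 has weight and edema monitoring. Section 12.3.14 sets a limit: "No more than a total gain of 15% weight gain if associated with signs and symptoms of volume overload", but it sits among the reporting waivers and names no action. Section 10.4 allows emergency unblinding, and 12.3.19 provides for study-level review. None of these requires an individual's drug to be stopped after a Grade 4 event.

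**Step 5: comparison with item 7.** Section 12.2.2.6 says that the insert already carries reports of hepatic failure. Item 7 nevertheless stops drug on a persistent rise without another cause, whether or not it was expected. Item 3 applies a different principle to other organs.

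**Step 6: a rough guide to frequency.** Section 6.6 reports 16 serious events in the rheumatoid arthritis trial: 1 probably related, 5 judged not related, and 16 − 1 − 5 = 10 definitely not related. Table 2 gives 129 subjects on pioglitazone. At most 1/129 = 0.8% (exact 95% CI 0.02% to 4.2%) would have met item 3 without the expectedness condition through a serious event. With all 143 enrolled as denominator, the figure is 1/143 = 0.7% (0.02% to 3.8%). Grades are not reported, non-serious Grade 4 laboratory events are not counted, and the population differs. This indicates rarity; it is not an estimate for this trial.

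**The case against.** The best defence has three parts.

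First, hepatic failure, one of the main life-threatening risks described, is already covered by item 7. This stands, and the point is limited to non-hepatic events.

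Second, the severity clause in 12.3.8.3 probably makes new life-threatening heart failure or fluid overload unexpected, because the protocol describes only milder forms or worsening of existing failure. This largely stands. What remains is that a mandatory stop turns on how the investigator reads that clause, and on how the package insert words its warnings. The insert is not among the documents.

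Third, item 6 is itself a required stop, and few investigators would find an immediate risk of death acceptable. In the rheumatoid arthritis trial, the one probably related serious event resolved when drug was stopped, and drug was also stopped for an event judged not related. This is fair. It also means that the amended wording would change little in practice while removing a source of variation. Some discretion would remain, since relatedness is also the investigator's judgement.

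A reader might infer that the protocol lets subjects continue drug after life-threatening heart failure, or that known toxicities in general escape the stopping rules. The documents do not support either reading: items 6 and 7 and the severity clause all stand in the way.

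**Conclusion.** The point holds in a narrow form. For a related, non-hepatic Grade 4 event that the investigator classes as expected, Section 10.1 leaves stopping to the investigator's opinion under item 6. The cause is a reporting term used as a safety condition, which item 7 does not do.

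The conclusion assumes that 'unexpected' in item 3 carries the 12.3.8.3 meaning, the only one the protocol gives. It also assumes that at least some Grade 4 events could reasonably be read as described in the insert or protocol.

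The number of subjects affected cannot be estimated and is likely to be small. This is a safeguard for a rare event, with no bearing on power, type I error or the treatment estimates. It should be changed because the change is nearly free.

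**What to change.** Delete the words 'unexpected and' from item 3 of Section 10.1, so that the stop depends on grade and relatedness alone. Leave 12.3.8.3 and 12.3.14 as they are, as reporting rules. No new procedure or visit is needed.

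The cost is possibly a few extra discontinuations, such as an expected, transient Grade 4 laboratory change judged possibly related. Section 12.3.6 limits these: a laboratory change counts as an adverse event only if the investigator considers it clinically significant, and the criteria for that refer to a dosing change or treatment and to the absence of another explanation. The number cannot be derived from the documents.

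The design has some room. Section 11.1 already plans for 20% dropout, and 100 × (1 − 0.20) = 80 is 5 above the target of up to 75 completers in Section 8. The margin is smaller to the extent that screen failures use enrolment slots. Under 10.2, subjects who complete only one arm are replaced and still analysed.
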